## Protocol Synopsis

---

# Intravenous Iron supplement for Iron deficiency in Cardiac transplant recipients: The IronIC trial

Sponsor	Oslo University Hospital
Phase and study type	Phase II, interventional, randomised controlled trial
Investigational Medical Product (including active comparator and placebo) :	Intravenous iron isomaltoside or matching placebo (NaCl 0.9 %)
Centres:	Oslo University Hospital, Rikshospitalet, Oslo, Norway
Study Period:	Estimated date of first patient enrolled (study start): February 1 st 2018 Anticipated recruitment period: February 1 st 2018 – January 31 st 2019 Estimated date of last patient completed (last patient, last visit: Study end): July 30 th 2019
Treatment Duration:	1 day
Follow-up:	6 months
Objectives	
The main goal of this study is to evaluate the effect of a single dose of intravenous iron isomaltoside on exercise capacity in cardiac allograft recipients with iron deficiency.
 
Secondary objectives are to assess the impact of treatment on: (i) iron stores, (ii) muscle strength, (iii) body composition, (iv) cognitive function, (v) quality of life, (vi) markers of myocardial disease and inflammation, and (vii) safety and tolerability.

Endpoints:	
Primary endpoint: The primary endpoint will be the between-group difference in the baseline-adjusted peak oxygen consumption measured 6 months after trial intervention.
 
Secondary endpoints:
 

• The number of patients with absolute or functional iron deficiency

• Muscle strength as measured by a hand-grip (device)

• Body composition

• Quality of life as assessed by the SF-36 and EQ 5D 3L EuroQoL questionnaires

• Cognitive function

• N-terminal pro-B-type natriuretic peptide (NT-proBNP)

• Cardiac troponin T (TnT)

• C-reactive protein (CRP)

- Inflammatory and vasoactive peptides

Study Design:	This is a single site, dual arm, double blind, randomised, placebo controlled trial.
Main Inclusion Criteria:	
Heart transplant recipient.
 
Iron deficiency defined as serum ferritin < 100 µg/l or ferritin between 100 and 300 µg/l in combination with a transferrin saturation < 20 %.
 
Age between 18 and 80 years.
 
Signed informed consent and expected compliance with protocol.

Main Exclusion Criteria	
Contraindications to study medication.
 
Failure to obtain written informed consent

Sample Size:	100 patients
Efficacy Assessments:	Assessment of peak oxygen consumption; biomarkers reflecting iron stores and metabolism, myocardial stress, and inflammation; muscle strength, cognitive function and quality of life
Safety Assessments:	Physical examination. In-hospital observation for at least two hours after study drug administration. Safety visit at general practitioner 3 months after study drug administration. A 24-hour contact number will be provided. Repeat assessment after six months.

## List of abbreviations and definition of terms

Abbreviation or special term	Explanation
AE	Adverse event
CANTAB	Cambridge Neuropsychological Test Automated Battery
CRF	Case report form (electronic/paper)
CRP	C-reactive protein
DMC	Data monitoring committee
GCP	Good clinical practice
ICH	International Conference on Harmonisation
NT-proBNP	N-terminal pro-B-type natriuretic peptide
SAE	Serious adverse event
SUSAR	Suspected unexpected serious adverse reaction
TnT	Cardiac troponin T

# 1 Introduction

---

Heart transplantation is the treatment of choice for selected patients with end-stage heart failure. World-wide, the median survival after transplantation is approximately 11 years. Early survival is limited by early graft failure and acute rejections, whereas complications to immunosuppressive therapy, such as infections and cancers, are among the most important causes of death in long-term survivors. On the other hand, a major impediment to long-term survival is cardiac allograft vasculopathy caused by smouldering rejection. Long-term success in heart transplantation is therefore dependent on compromising between detrimental immunosuppression and low-grade inflammation.

Iron is an essential nutrient and co-factor not only in haemoglobin, but in several key respiratory reactions. It readily engages in one-electron oxidation-reduction reactions between its ferric (3+) and ferrous (2+) states. We exploit this property in oxidative phosphorylation, where iron acts as an intermediate in the electron transport chain. However, the same chemical quality explains why an excess of free, reactive iron is toxic. Ferrous iron can participate in redox chemistry known as the Fenton reaction, where it reacts with hydrogen peroxide or lipid peroxides to generate ferric iron, OH, and highly reactive radicals. These compounds damage lipid membranes, proteins, and nucleic acids. Since cellular iron overload as well as iron deficiency are detrimental, the levels of reactive iron must be carefully controlled and limited.

Exercise capacity and health-related quality of life are reduced in cardiac allograft recipients despite good over-all results regarding graft function. We have shown exercise capacity after heart transplantation depends mainly on peripheral factors rather than on allograft function. Numerous mechanisms unrelated to haemodynamic dysfunction may underlie the impaired exercise tolerance in heart transplant recipients, one of which may be iron deficiency. Iron plays a key role in oxygen uptake, transport, storage, and metabolism in skeletal muscle. Heart transplant recipients have multiple reasons for having iron deficiency, including previous heart failure, perioperative blood loss, frequent blood sampling, renal failure, and polypharmacy. Among our heart transplant survivors, 48 % have iron deficiency (defined as serum ferritin < 100 µg/l or ferritin between 100 and 300 µg/l in combination with a transferrin saturation < 20 %) [Abstract submitted to ISHLT congress, Nice 2018]. We hypothesise that intravenous iron therapy will improve peak oxygen consumption, muscle strength, functional capacity and quality of life in these patients. The IronIC trial is designed to test this hypothesis.

## 1.1 Iron metabolism

---

Dietary iron is absorbed in the small intestine and transferred to the circulation. Before absorption, ferric iron in the diet must be reduced to ferrous iron at the apical surface of enterocytes. Iron is then transported into the cell by the divalent metal transporter-1, an energy-dependent symporter that is essential for intestinal uptake of inorganic sources of dietary iron. Heme, another source of dietary iron, is internalised through receptor-mediated endocytosis. This process seems to be regulated by iron stores. Ferrous iron is exported through the basolateral membrane of the enterocyte to the interstitial space by the exporter ferroportin and oxidised by the ferroxidase hephaestin. Ferroportin is negatively regulated by the iron-regulatory hormone hepcidin.

The major transport protein for circulating iron is transferrin. Once extracellular, iron is bound with high affinity by this protein. The cellular uptake of iron occurs through receptor-mediated endocytosis of the iron/transferrin complex through transferrin receptor-1. Iron is then exported from the endosomal vesicle by the divalent metal transporter-1, suggesting that a ferrireductase must exist within the endosomal vesicle. Ferrous iron is thought to enter a labile intracellular iron pool, from where it can be utilised for intracellular functions.

The portion of intracellular iron that is not needed for immediate use is stored by ferritin. Twenty-four ferritin subunits assemble to form the apoferritin molecule, each of which can sequester up to approximately 4500 iron atoms. Ferritin also possesses enzymatic properties, and oxidises

ferrous iron to its ferric form. Small amounts of iron-poor ferritin are present in the serum, where it can be measured and quantified. Serum ferritin is elevated in iron overload, but also in inflammatory conditions.

The content of cytoplasmic ferritin is regulated by the availability of intracellular free iron. This regulatory response is posttranscriptional. When intracellular iron stores are depleted, iron regulatory proteins 1 and 2 bind to the iron responsive element of the ferritin mRNA and prohibit translation. Conversely, when iron levels are high, ferritin synthesis increases. On the contrary, the binding of iron regulatory proteins to an iron regulatory element in transferrin receptor 1 mRNA lengthens its half-life, ultimately leading to increased transferrin receptor display on the cell surface in situations of iron depletion.

Ferritin and transferrin, established markers of iron availability, are regulated not only by iron stores, but also by inflammation. Ferritin is an “acute phase” protein, the serum concentrations of which increase in inflammatory conditions. In fact, ferritin can be viewed not only as an iron regulatory protein, but also as a protein that takes part in the cellular defence against stress and inflammation. Transferrin receptor-1 and transferrin, on the other hand, are down-regulated in inflammatory states. These responses contribute to low available iron in states of inflammation, presumably to deprive invading microorganisms of an essential nutrient.

The major regulator of systemic iron metabolism is the peptide hormone hepcidin. Full iron stores induce hepcidin transcription through the bone morphogenetic protein signalling pathway. However, hepcidin expression is also up-regulated in inflammation. Its mode of action is to bind to, and induce degradation of, ferroportin. Hepcidin thus exerts its control over systemic iron metabolism by regulating the transfer of dietary, recycled, and stored iron from intracellular compartments to the extracellular fluid, regulating the amount of iron available for iron-demanding tissues. This gate-keeping mechanism reduces the effect of oral iron in patients with inflammation, and can be partially circumvented by intravenous administration of iron.

## 1.2 Iron deficiency in heart failure

---

Iron deficiency is prevalent in patients with heart failure. Iron deficiency is associated with a worse prognosis, and randomised controlled trials have shown that correction of iron deficiency with intravenous iron therapy improves functional capacity, quality of life, and 6-minute walk distance. Current guidelines therefore recommend intravenous iron substitution in patients with heart failure with reduced ejection fraction and iron deficiency. Intravenous iron is more effective, better tolerated, and improves quality of life to a greater extent than oral iron supplements. In the IRONOUT HF trial, in which 225 patients with systolic heart failure were randomised to oral iron supplement or placebo, there was no effect on oxygen uptake, 6-minute walk distance, or quality of life. The authors attributed the negative results to the minimal effect on iron stores, suggesting that oral iron does not adequately replenish iron stores in patients with heart failure.

Cardiac allograft recipients resemble patients with heart failure in many respects. Prior to transplantation, and in some instances after heart transplantation, they have had overt heart failure. Moreover, due to the immunologic challenge posed by the allograft, and their susceptibility to infection due to immunosuppressive treatment, cardiac allograft recipients have low-grade inflammation. This low-grade inflammation makes it difficult to interpret iron stores, and results in dysregulated iron metabolism.

To our knowledge, there have been no studies to assess the effect of intravenous iron therapy in heart transplant recipients who have iron deficiency. There is reason to believe that a liberal definition of iron deficiency should be used in cardiac allograft recipients, and we have elected to use the well-established definition used in patients with heart failure: serum ferritin < 100 µg/l or ferritin between 100 and 300 µg/l in combination with a transferrin saturation < 20 %. Because oral iron supplement is less effective than intravenous iron in general, and in patients with heart failure in particular, we assume that oral iron supplement is inadequate in heart transplant recipients. We

have designed the IronIC trial to assess the effect of intravenous iron isomaltoside on exercise capacity, muscle strength, cognition and quality of life in iron-deficient heart transplant recipients.

### 1.3 Therapeutic information

---

Isomaltoside 1000 is an oligosaccharide with a mean molecular weight of 1,000 Da, which consists predominantly of unbranched chains corresponding to 3–5 glucose units. The iron in Monofer® is tightly bound to isomaltoside in a matrix containing approximately 10 iron molecules per one isomaltoside pentamer. This structure releases iron to iron-binding proteins in a controlled manner with little risk of free iron toxicity.

#### 1.3.1 Pre-Clinical & Clinical Experience with iron isomaltoside

---

According to the Summary of Product Characteristics (SPC), available at [www.medicines.org.uk](http://www.medicines.org.uk), iron complexes have been reported to be teratogenic and embryocidal in non-anaemic pregnant animals at high single doses above 125 mg iron/kg body weight. The highest recommended dose in clinical use is 20 mg iron/kg body weight. In a murine fertility study with Monofer®, there were no effects on male reproductive performance and spermatogenic parameters. There have been no adequately sized and controlled trials to assess the safety of iron isomaltoside in pregnancy, and Monofer® should not be used in pregnancy unless clearly necessary. Iron does not transfer easily to human milk, and no adverse effects on breastfed infants are anticipated. In patients with chronic kidney disease, the plasma iron half-life is approximately 30 hours after intravenous administration, regardless of the infused dose. After infusion, the iron in iron isomaltoside follows first-order kinetics.

Clinical experience with Monofer® has been reviewed by Kalra and Bhandari. In short, the efficacy and safety of intravenous iron isomaltoside has been investigated in patients with chronic kidney disease, inflammatory bowel disease, and postpartum haemorrhage. In general, the treatment has been efficacious and associated with few adverse events. In a double-blind trial, 60 patients undergoing coronary bypass surgery were randomised to receive 1000 mg iron isomaltoside (up to 20 mg/kg body weight) or saline. The fall in haemoglobin was significantly less pronounced in patients allocated to iron. No adverse events were observed. In 20 patients with congestive heart disease and iron deficiency anaemia who received on average 868 mg (range 650–1000 mg) of iron isomaltoside, there was a significant improvement in health-related quality of life and no serious adverse events. Specifically, there were no acute or delayed hypersensitivity reactions.

#### 1.3.2 Known and potential risks and benefits

---

Intravenous iron transfusion carries a very low, but clinically significant risk of hypersensitivity reactions. This risk is increased in patients with known allergies, an allergic diathesis, or autoimmune diseases. Heart transplant recipients are treated with immunosuppressants and possibly less prone to experiencing these reactions. To prevent serious consequences of a hypersensitivity reaction, the patients will be monitored in-hospital during the study drug infusion and for at least two hours afterwards. The Monofer® SPC specifically recommends at least 30 minutes of observation. The infusions will be administered at the cardiology ward at Rikshospitalet. This ward is well-staffed and equipped to deal with acute hypotension/cardiac arrest/respiratory failure. Hypersensitivity-reactions should be treated with immediate stop in transfusion, volume resuscitation, and supportive care and cardiopulmonary resuscitation as required. The investigator and the responsible physician must decide whether reintroduction of the study drug infusion is safe after the episode has been resolved, depending on the severity of the episode. Nominal hypotension without symptoms and without threatening organ function is acceptable and should not result in study drug withdrawal.

Subcutaneous/extravenous infusions can lead to skin reactions and prolonged discolouration of the skin. Vigilant assessment of the infusion site is therefore necessary during drug infusion, and careful testing of the peripheral cannula with infusion of a test dose of isotonic saline should be performed prior to study drug infusion.

The benefit of intravenous iron supplement in iron-deficient heart transplant recipients is unknown. Experience from other populations, and from patients with heart failure in particular, suggests that intravenous iron can replete iron stores and improve exercise capacity and health-related quality of life in patients with iron deficiency. This trial is designed to assess if similar results can be obtained in iron-deficient heart transplant recipients.

#### 1.4 Rationale for the study and purpose

---

Iron deficiency is associated with poor exercise capacity, lethargy and reduced quality of life. Our results show that iron deficiency is prevalent in heart transplant recipients. Cardiac allograft recipients have reduced exercise capacity and quality of life compared with the age and gender matched general population. We assume that some of these symptoms are due to iron deficiency, and hypothesise that intravenous iron supplement will improve peak oxygen consumption, muscle strength, functional capacity, cognition, and health-related quality of life in heart transplant recipients with iron deficiency.

#### 1.5 Rationale for study endpoint

---

Measurement of peak oxygen capacity is the gold standard for assessing exercise capacity. Exercise capacity is an established surrogate endpoint in patients who are evaluated for heart transplantation. Exercise capacity is associated with mortality before and after heart transplantation, and is tightly associated with quality of life in these patients. We have extensive experience in measuring peak oxygen uptake in heart transplant recipients. Moreover, the accuracy of this measurement is good, resulting in low intra-individual variability in repeated measurements.

## 2 Study objectives and related endpoints

---

The main goal of this study is to evaluate the ability of a single administration of intravenous iron isomaltoside to increase peak oxygen consumption in cardiac allograft recipients who have iron deficiency defined as serum ferritin < 100 µg/l or ferritin between 100 and 300 µg/l in combination with a transferrin saturation < 20 %.

Secondary objectives are to assess the impact of treatment on: (i) iron stores, (ii) muscle strength, (iii) body composition, (iv) cognitive function, (v) quality of life, (vi) markers of myocardial disease and inflammation, and (vii) safety and tolerability.

#### 2.1 Primary endpoint

---

The primary endpoint will be the baseline-adjusted between-group difference in peak oxygen consumption as measured on a treadmill exercise test 6 months after study drug administration.

#### 2.2 Secondary endpoints

---

[figure not shown]
Secondary endpoints:

- The number of patients with absolute or functional iron deficiency
- Muscle strength as measured by a hand-grip dynamometer
- Body composition
- Cognitive function as assessed by the Cambridge Neuropsychological Test Automated Battery
- Quality of life as assessed by the SF-36 and 5D EuroQoL questionnaires
- N-terminal pro-B-type natriuretic peptide (NT-proBNP)
- Cardiac troponin T (TnT)
- C-reactive protein (CRP)

- Inflammatory and vasoactive peptides

### 3 Overall study design

This is a phase 2, double blind, randomised, placebo-controlled trial. Participants will be randomised in a 1:1 fashion to receive a single intravenous dose of iron isomaltoside or matching placebo. The study is designed to show superiority with regard to the primary endpoint in patients assigned to active treatment versus patients allocated to the placebo arm.

#### Study Period

Estimated date of first patient enrolled (study start): February 1st 2018.

Anticipated recruitment period: February 1st 2018 – January 31th 2019.

Estimated date of last patient completed (last patient, last visit: Study end): August 1st 2019.

#### Treatment Duration:

One day (single iv dose drug administration)

#### Follow-up:

6 months

### 4 Study population

#### 4.1 Selection of study population

The IRONIC trial will be conducted at Oslo University Hospital, Rikshospitalet, in Oslo, Norway. Oslo University Hospital Rikshospitalet is the only centre in Norway to perform transplants. We perform approximately 35 heart transplants per year. With a median survival of more than 12 years, we have a population of approximately 500 cardiac allograft recipients who attend regular follow-ups twice per year. Per routine, we measure ferritin and transferrin saturation in all of these patients. We plan to recruit patients who are admitted for their yearly control, and who have iron deficiency defined as serum ferritin < 100 µg/l or ferritin between 100 and 300 µg/l in combination with a transferrin saturation < 20 %. A dedicated study nurse will send a written invitation to participate in the trial prior to the patient's routine control at our centre.

#### 4.2 Number of patients

We aim to enrol 100 patients in this trial.

#### 4.3 Inclusion criteria

---

Patients will be screened for eligibility upon admittance for routine follow-up at least one year after heart transplantation.

All of the following conditions must apply prior to administering the investigational medicinal product:

- Cardiac allograft.
- Presentation at least one year after heart transplantation.
- Iron deficiency defined as serum ferritin < 100 µg/l or ferritin between 100 and 300 µg/l in combination with a transferrin saturation < 20 %.
- Age between 18 and 80 years.
- Informed consent obtained and documented according to Good Clinical Practice (GCP), and national/regional regulations.

#### 4.4 Exclusion criteria

---

Patients will be excluded from the study if they meet any of the following criteria:

- Anaemia (Haemoglobin < 100 mg/l)
- Haemochromatosis
- Haemosiderosis
- Porphyria cutanea tarda
- Blood dyscrasias or any disorders causing haemolysis or unstable red blood cells
- Decompensated liver disease (Child-Pugh score 7 or higher)
- End-stage renal failure, i.e. eGFR < 15 ml/min or on renal replacement therapy
- Planned cardiac surgery or angioplasty within 6 months
- Planned major surgery within 6 months
- Medical history of unresolved cancer (except for basal cell carcinoma)
- Treatment with systemic steroids more than the equivalent of 10 mg Prednisone/day at the time of informed consent or change in dosage of thyroid hormones within 6 weeks prior to informed consent
- Any uncontrolled endocrine disorder except type 2 diabetes
- Pregnancy
- On erythropoietin analogues
- Known sensitivity or intolerance to iron isomaltoside or other parenteral iron preparations
- Intravenous iron supplement within 6 months prior to inclusion
- On oral iron substitution (unless the subject agrees to stop treatment prior to randomisation)
- Ongoing rejections or infections
- Alcohol or drug abuse within 3 months of informed consent that would interfere with trial participation or any ongoing condition leading to decreased compliance with study procedures or study drug intake
- Intake of an investigational drug in another trial within 30 days prior to intake of study medication in this trial or participating in another trial involving an investigational drug and/or follow-up

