## 5.3 Duration of therapy

---

The investigational medicinal products (iron isomaltoside or placebo) will be administered as a single intravenous infusion over 30 minutes only (1,67 ml/min). No other study-specific intervention will be provided. For intravenous iron, a single dose of 20 mg/kg is expected to provide adequate iron supplement in patients with haemoglobin above 100 mg/l.

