7.3 Covariates and Subgroups

The primary analyses (intention-to-treat population) will not be adjusted for baseline demographics. However, the primary endpoint and key secondary endpoints are calculated as the baseline-adjusted values (i.e. the follow-up result is adjusted for the baseline result of the same assessment in ANCOVA analyses) as specified for each endpoint.

We will perform binary subgroup analyses of the primary endpoint stratified by gender; age (median); whether the baseline transferrin saturation is $<$ or \geq 20 %; by whether or not the patient has anaemia (defined according to World Health Organization criteria of $<$ 12 g/l for women and $<$ 13 g/l for men); C-reactive protein (median) and whether or not iron parameters have normalised (to values no longer defined as iron deficiency as defined in "study objectives"). A forest plot will be used

to communicate the results. The subgroup analyses are exploratory only, as the trial is not powered to show differences across subgroups.

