7.4 Missing Data

Because the efficacy data are collected twice only, and the endpoint analyses will be baseline adjusted ANCOVA or single point assessments only, there will be no imputation of missing data. However, to elucidate possible biases this method entails, baseline data for patients for whom endpoint data exist will be compared with baseline data for patients who for some reason drop out or are unable to complete both sets of tests. We will also explore if the dropout rate differs between the treatment arms. The extent of missing data will be quantified for each endpoint variable.

We expect few missing baseline covariates and will not employ a strategy to impute missing baseline covariates.

8 Summary of Study Data

The baseline, intention-to-treat population demographics will be presented by columns for each treatment (Placebo, Intravenous iron isomaltoside). All continuous variables will be summarised using the following descriptive statistics: mean \pm standard deviation; median (interquartile range). The frequency and percentages (based on the non-missing sample size) of observed levels will be reported for all categorical measures. All summary tables will be structured with a column for each treatment in the order (Control, Experimental) and will be annotated with the total population size relevant to that table/treatment, including any missing observations.

The sample size of non-missing values for univariable summary statistics may be larger than the sample size of non-missing values in a complete-case analysis used in the primary regression (ANCOVA) analysis.

Table 1

Demographics	Placebo	Intravenous iron
Age – years		
Male gender – no (%)		
Time since HTx – years (IQR)		
Reason for HTx, no (%)		
Ischemic		
DCMP		
GUCH no		
Other no		
Left ventricular ejection fraction		
NYHA functional class, no (%)		
I		
II		
III		
IV		
Body mass index – kg/m ²		

Systolic blood pressure – mmHg

Heart rate – beats per minute

Treatment

Cyclosporine/Tacrolimus

Everolimus

Mycophenolic acid/Azathioprine

Prednisolone

Angiotensin converting enzyme inhibitor

Angiotensin II-receptor antagonist

Loop diuretic

Thiazide

Beta-blocker

Calcium antagonist

Platelet inhibitors

Oral anticoagulants

Proton pump inhibitors

Biochemistry

Haemoglobin – g/l

Creatinine - μ mol/L

Estimated glomerular filtration rate – ml/min/1.73m²

Ferritin – μ g/l (IQR)

Transferrin saturation – % (IQR)

Transferrin receptor (mg/l) % (IQR)

Sedimentation Rate – mm (IQR)

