9.2 Secondary Efficacy Analyses

Secondary, per protocol analysis will be performed for the primary endpoint. Exploratory subgroup analyses will be performed for the six subgroup categories mentioned in the section “Covariates and subgroups. The latter results will be communicated as a forest plot, and the interaction value of the covariates “treatment allocation” and the binary subgroup identifier in question will be reported at a significance level of 0.05.

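### The haemoglobin thresholds for the anaemia exclusion and the anaemia subgroup carry the wrong units as written, by different factors

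*Protocol*

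**What the plan says.** Four places set or use a haemoglobin cut, and a fifth fixes the reporting unit.

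- Protocol 4.4 lists as an exclusion "Anaemia (Haemoglobin < 100 mg/l", and SAP 5.3.2 repeats the criterion with the same number and unit.
- Protocol 5.3 says that "a single dose of 20 mg/kg is expected to provide adequate iron supplement in patients with haemoglobin above 100 mg/l".
- SAP 7.3 splits the primary endpoint "by whether or not the patient has anaemia (defined according to World Health Organization criteria of" less than 12 g/l for women and less than 13 g/l for men.
- SAP section 8, Table 1 lists "Haemoglobin – g/l" among the baseline variables.

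SAP 9.2 adds that "Exploratory subgroup analyses will be performed for the six subgroup categories" listed in 7.3, with a forest plot and each interaction reported at the 0.05 level. SAP section 12 states that the SAP departs from the protocol only in its level of detail and in specifying the subgroups. Neither document gives any of these thresholds in another unit or corrects one.

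**The concern.** An eligibility threshold and a prespecified subgroup threshold are working rules: someone checks a patient against the first and programs the second. Both are written in units that put them far below any haemoglobin seen in an ambulatory patient.

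For eligibility, the criterion taken literally does not do what its label, anaemia, says it should. A screener who does exclude a patient for low haemoglobin is applying a rule that the text does not contain. This has formal consequences. Protocol 6.3 lists failure to meet the entry criteria as a ground for discontinuation, and protocol 9.2 requires the medical record to hold the results that confirm eligibility. Protocol 5.3 attaches its expectation about the single 20 mg/kg dose to the same misstated figure, so that sentence cannot be read as intended either.

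For the analysis, a subgroup indicator coded from 12 and 13 on a g/l scale would be constant. Its interaction with treatment could not be estimated, and one line of the forest plot would have no patients on one side. If the cut were changed only after the code had been opened, that subgroup could no longer be called prespecified.

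**Working it through.** **The plan's own figure.** The one computed design figure is the sample size (protocol 10.1, SAP section 6): difference 1.5 ml/kg/min, SD 2.5 ml/kg/min, power 80 %, two-sided α 5 %.

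n per group = 2 × (1.960 + 0.842)² × (2.5 / 1.5)² = 2 × 7.85 × 2.78 = 43.6, rounded up to 44.

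This reproduces the stated 44. No haemoglobin value enters the formula, so the point below does not touch it.

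**Unit conversion** (1 g/l = 1000 mg/l = 0.1 g/dl).

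| Rule | As written | In g/l | In g/dl |
|---|---|---|---|
| Exclusion (protocol 4.4, SAP 5.3.2) and dose expectation (protocol 5.3) | 100 mg/l | 100 / 1000 = 0.1 | 0.01 |
| Subgroup, women (SAP 7.3) | 12 g/l | 12 | 1.2 |
| Subgroup, men (SAP 7.3) | 13 g/l | 13 | 1.3 |

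**Share of patients each rule catches as written.** The documents give no haemoglobin distribution, so I assume a normal distribution with mean 110–140 g/l and SD 10–20 g/l. The largest probabilities arise at mean 110 and SD 20:

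- P(Hb < 0.1) = Φ((0.1 − 110) / 20) = Φ(−5.495) = 2.0 × 10⁻⁸
- P(Hb < 12) = Φ((12 − 110) / 20) = Φ(−4.90) = 4.8 × 10⁻⁷
- P(Hb < 13) = Φ((13 − 110) / 20) = Φ(−4.85) = 6.2 × 10⁻⁷

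Among 100 patients the largest expected count is 100 × 6.2 × 10⁻⁷ = 0.00006, which is nobody under either rule. A simple plausible range of 70–180 g/l gives the same answer, since all three cuts lie far below 70.

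**Does one correction repair both?** No.

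- If the exclusion numeral was meant in g/l, the unit is off by 100 / 0.1 = 1000.
- If the subgroup numerals were meant in g/dl, they are 120 and 130 g/l, off by 120 / 12 = 130 / 13 = 10.
- If only the exclusion is read as 100 g/l, the subgroup is still empty, because anyone below 12 or 13 g/l would already have been excluded.

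**Sensitivity to the unit.** Over the same assumed grid, a cut at 100 g/l would catch about 0–31 % of patients. Cuts at 120 and 130 g/l would catch about 2–84 % and 16–98 %, before any exclusion is applied. These figures show only how much the unit matters; they are not an argument for any threshold.

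**The case against.** The strongest reply is that these are obvious misprints. The criterion is labelled anaemia, the subgroup rule names the World Health Organization criteria, and Table 1 gives g/l. The trial has one centre, where eligibility is checked against routine blood results. Staff would probably apply the numeral 100 on the reporting scale, and an analyst who found every patient in one stratum would notice at once. If the data were held in g/dl, the numerals 12 and 13 would even divide patients sensibly. Much of this stands. It makes serious practical harm unlikely, but the documents do not record how the figures were applied, and the only unit they attach to reported haemoglobin is g/l.

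A reader might infer more than the text supports:

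- *That anaemic patients would in fact be enrolled.* The wording would allow it, but nothing shows that it would happen. A catch of nobody describes the literal rule under an assumed range, and does not predict enrolment.
- *That the single-dose design rests on this threshold.* Protocol 5.3 gives one sentence of expectation. Protocol 5.2 doses by body weight and cites the manufacturer's recommendation, and the sample-size section assumes nothing about haemoglobin.
- *That an exclusion cut 120 to 130 times lower than the subgroup cuts is a contradiction in itself.* It is not. An exclusion that removes the more anaemic patients should lie below the subgroup cut. The ratio only reflects the unit errors.
- *That efficacy conclusions are at risk.* The SAP says "The subgroup analyses are exploratory only, as the trial is not powered to show differences across subgroups", and the primary model contains only treatment and baseline peak oxygen consumption.

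**Conclusion.** The point holds as a units error in two operative rules. As written, the haemoglobin cut in protocol 4.4, protocol 5.3 and SAP 5.3.2 equals 0.1 g/l, and the SAP 7.3 cuts of 12 and 13 g/l are also out of reach. Taken literally, the exclusion removes no one. Coded literally on g/l values, the anaemia stratum is empty and one of six exploratory interactions cannot be estimated.

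This rests on one assumption from outside the documents: a plausible haemoglobin range for patients attending routine follow-up. The margin is wide enough that no reasonable range changes the result. The factors of 1000 and 10 depend on what the sponsor meant and are conditional on that.

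The primary ANCOVA, the 44 per group and the planned 100 patients are unaffected. The eligibility wording matters more than the subgroup, because it governs entry and appears in both documents.

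**What to change.** 1. Reconcile protocol 4.4, protocol 5.3 and SAP 5.3.2 with the g/l unit in SAP Table 1, so that all three carry one attainable figure. Which haemoglobin threshold is intended is for the sponsor to state.
2. Have the sponsor confirm the unit intended in SAP 7.3, then restate the cuts in g/l. If g/dl was meant, 12 and 13 g/dl convert to 120 and 130 g/l.
3. Make the SAP change before database lock and before the randomisation code is opened. Protocol 10.4 allows the statistical plan to be amended until lock.
4. Record which threshold was applied to patients already screened, so that eligibility can be checked against the rule actually used.

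The cost is corrected wording in three places for the exclusion figure and one for the subgroup, with the usual amendment notification for the protocol text, plus a short note on past screening. No extra patients, visits or measurements are needed.
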